3.5.5.4 Electrocardiogram

Standard 12-lead ECGs will be measured in triplicate on the site machines after the subject has been supine for at least 5 min at Screening, Baseline, T1 – Day 28, and T2 – Day 28 (Visit 19/EOS/ET). The ECG results will be documented in the eCRF.

3.5.5.5 Laboratory Parameters

The following clinical laboratory tests are to be performed at Screening, Baseline, T1 – Day 5, T1 – Day 28, T2 – Day 5, and T2 – Day 28 (Visit 19/EOS/ET) unless noted below:

Hematology: Hemoglobin, hematocrit, red blood cell count, WBC count (with differential [lymphocytes, neutrophils, eosinophils, basophils, and monocytes]), and platelet count.

Serum Chemistry: albumin, alkaline phosphatase, AST, ALT, direct bilirubin, total bilirubin, blood urea nitrogen, calcium, chloride, creatine kinase (Screening only), creatinine, gamma-glutamyl transferase, glucose, lactate dehydrogenase, potassium, sodium, and uric acid.

Other tests: HbA1c, HIV, hepatitis B, and hepatitis C at Screening. Coagulation tests at Screening or Baseline: activated PTT, PT, and INR. Coagulation tests may be repeated prior to the index and repeat injection, if deemed necessary by the Investigator.

Urinalysis: Dipstick analysis: color, turbidity, specific gravity, pH, glucose, protein, ketones, urobilinogen, bilirubin, blood nitrate, leukocyte esterase, and microscopic examination when indicated by dipstick results.

Urine drug screen: Includes opiates, barbiturates, benzodiazepines, tricyclic antidepressants, cannabinoids, PCP, cocaine, ecstasy, and amphetamines. A urine drug screen will be obtained at Screening, Baseline, and T1 – Day 28. A urine drug screen may be repeated if deemed necessary by the Investigator.

WOCBP: Serum pregnancy test at Screening. Urine pregnancy test at Baseline and at Visit 11 (T2 – Day 0). A urine pregnancy test may be repeated if deemed necessary by the Investigator.

Laboratory samples will be analyzed by the local laboratory. In the event of an unexplained clinically noteworthy abnormal laboratory test value, the test should be repeated immediately and followed up until it has returned to the normal range and/or an adequate explanation of the abnormality is found.

3.5.5.6 Adverse Events

All AEs occurring after the subject signs the ICF through EOS/ET (Visit 19) will be recorded.

See [Section 4](#) for additional information.

3.5.6 Appropriateness of Measurements

All assessments to be used in this study are commonly used, standard measurements frequently seen in radiculopathy studies.

4 ADVERSE EVENT REPORTING

Throughout the course of the study, after signing the ICF, all AEs will be monitored and recorded on an AE eCRF, including the AE's description, start and end date, seriousness, severity, action taken, and relationship to the IP. If AEs occur, the first concern will be the safety of the study subjects. All AEs will be followed until resolved or stable and the outcome documented on the eCRF.

4.1 Definitions and Criteria

4.1.1 Adverse Events

An AE is any untoward medical occurrence in a subject or clinical investigation subject administered a pharmaceutical product and which does not necessarily have to have a causal relationship with this treatment (ICH-E2A-1994). An AE can therefore be any unfavorable and unintended sign (including an abnormal laboratory finding, for example), symptom, or disease temporally associated with the use of a medicinal product, whether considered related to the medicinal product or not.

Medical interventions such as surgeries, diagnostic procedures, and therapeutic procedures are not AEs, but the action taken to treat the medical condition. They should be recorded as treatment of the AEs.

4.1.2 Serious Adverse Events

A serious adverse event (SAE) or reaction is any untoward medical occurrence that at any dose:

- Results in death
- Is life-threatening
- Requires inpatient hospitalization or prolongation of existing hospitalization
- Results in persistent or significant disability or incapacity
- Is a congenital anomaly or birth defect
- Is an important medical event (eg, intensive treatment in an emergency room or at home for allergic bronchospasm; blood dyscrasias, or convulsions that do not result in hospitalization; or development of drug dependency or drug abuse; malignancy tumors [histologically different from primary tumor])

Note: The term "life-threatening" in the definition of "serious" refers to an event in which the subject was at risk of death at the time of the event; it does not refer to an event that hypothetically might have caused death if it were more severe.

Medical and scientific judgment should be exercised in deciding whether expedited reporting is appropriate in other situations, such as important medical events that may not be immediately life-threatening or result in death or hospitalization but may jeopardize the subject or may require intervention to prevent one of the other outcomes listed in the definition above. These should also usually be considered serious.

Examples of such events are intensive treatment in an emergency room or at home for allergic bronchospasm; blood dyscrasias, or convulsions that do not result in hospitalization; or development of drug dependency or drug abuse.

Seriousness (not severity) serves as a guide for defining regulatory reporting obligations. An SAE is not necessarily severe; eg, an overnight hospitalization for a diagnostic procedure must be reported as an SAE even though the occurrence is not medically serious. By the same token, a severe AE is not necessarily serious: nausea of several hours' duration may be rated as severe but may not be considered serious.

4.1.3 Unexpected Adverse Drug Reactions

An unexpected adverse drug reaction (ADR) is a reaction for which the nature or severity is not consistent with the applicable product information (IB, [SP102-IB-2017](#)). Until product information is amended, expedited reporting is required for additional occurrences of the reaction. Reports that add significant information on specificity or severity of a known, already documented SAE constitute unexpected events. For example, an event more specific or more severe than described in the IB would be considered "unexpected." Specific examples would be (a) acute renal failure as a labeled ADR with a subsequent new report of interstitial nephritis and (b) hepatitis with a first report of fulminant hepatitis.

Guidance on reporting AEs and SAEs is described in [Section 4.2](#).

4.1.4 Abnormal Laboratory Values

Any abnormality ([Appendix H](#)) in a laboratory value that is new in onset or which has worsened in severity or frequency from the baseline condition and meets 1 of the following criteria will be recorded on the AE pages of the eCRF:

- Requires therapeutic intervention or diagnostic tests
- Leads to discontinuation of IP
- Has accompanying or inducing symptoms or signs
- Is judged by the investigator as clinically significant

4.1.5 Assessing Intensity and Relationship

All AEs will be assessed on 2 descriptive parameters: intensity and relationship to the IP:

- Intensity refers to the severity of an event and references impact on a subject's functioning.
- Relationship refers to the likelihood that the event being assessed was caused by the IP.

Intensity

Each AE will be classified according to [Appendix H](#).

When changes in the intensity of an AE occur more frequently than once a day, the maximum intensity for the experience should be noted. If the intensity category changes over a number of days, those changes should be recorded separately (with distinct onset dates).

Relationship

Each AE will be assessed as to its relationship to the IP, based on the following criteria. Although the attribution by the investigator will be collected for reported events, for analytic purposes a temporal association with the use of the IP will be assumed sufficient for at least plausible association.

Investigators are required to assess the causal relationship (ie, whether there is reasonable possibility that the study drug caused the event) using the following definitions:

- Unrelated: A clinical event, including laboratory test abnormality, with a temporal relationship to study drug administration that makes a causal relationship improbable, and/or in which other drugs, chemicals or underlying disease provide plausible explanations of the event.
- Possibly Related: A clinical event, including laboratory test abnormality, with a reasonable time sequence to administration of the study drug, but that could also be explained by concurrent disease or other drugs or chemicals. Information on study drug causality may be lacking or unclear.
- Probably Related: A clinical event, including laboratory test abnormality, with a reasonable time sequence to administration of the study drug, unlikely to be attributed to concurrent disease or other drugs or chemicals, and that follows a clinically reasonable response on re- administration (rechallenge) or withdrawal (dechallenge) of the study drug.
- Definitely Related: A clinical event, including laboratory test abnormality, with a temporal relationship to study drug administration that makes a causal relationship definite and is clearly related to use of the IP.

When assessing the relationship to the IP, the following criteria will be considered:

- Positive rechallenge
- Positive dechallenge (resolution upon stopping suspect the IP, in absence of other intervention or treatment)
- Known class effect
- Biological plausibility
- Lack of alternative explanation—concomitant drug or disease

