3.3.3 Stopping Rules

A single occurrence of an adverse event of special interest (AESI) ([Section 4.2.2](#)) precludes the subject from receiving a repeat injection. Three occurrences of the AESI of the same type across the study will trigger stopping of all further dosing until implementation of a safety review.

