7.12.1 Adverse Events

All AEs will be coded using the most current version of MedDRA. TEAEs and SAEs will be summarized descriptively for each treatment period.

A treatment emergent adverse event (TEAE) phase is defined as meeting either of the following 2 criteria:

- Any AE that has an onset on or after the index injection and within (after) 30 days of the last study treatment.
- Any pre-existing AE that has worsened in severity on or after the index injection and within (after) + 30 days of the last injection.

TEAEs for each treatment period, will be assessed as follows:

- A TEAE will be assigned to the treatment received immediately before onset.
- If the severity of a TEAE increases in a later period the TEAE at the increased severity will be assigned to the treatment received immediately before the increase in severity.

Onset date of adverse events on or post visit 3 but before visit 11 were considered as occurring during T1; otherwise onset date of adverse events on or post visit 11 were considered as occurring during T2

A treatment-related AE is defined as an AE as being possibly, probably or related to the study drug. If an AE has missing relationship it is assumed to be related to the study drug for analysis purposes.

Severity is classified as mild/moderate/severe/life-threatening/death (last two grades applied for SAE). If a subject reports AEs more than once within a SOC/PT, the AE with the worst-case severity will be used in the corresponding severity summaries. TEAE summary tables (except the overall summary table) will be presented by severity and overall.

The following tables will be presented by severity and overall for AEs:

- Overall incidence and the number of AEs, SAEs, TEAEs leading to withdrawal.
- Treatment-Emergent Adverse Event by System Organ Class and Preferred Term
- Related Treatment-Emergent Adverse Event by System Organ Class and Preferred Term
- Serious Treatment-Emergent Adverse Events by System Organ Class and Preferred Term
- Serious Treatment Related Treatment-Emergent Adverse Events by System Organ Class and Preferred Term
- Treatment Discontinued Treatment-Emergent Adverse Events by System Organ Class and Preferred Term
- Summary of Treatment-Emergent Adverse Events Leading to Death

All AEs will be listed.

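### One adverse event is split into dated intensity records with no rule for rejoining them, so the AE count can be inflated and an easing T1 event can be counted in T2

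*Protocol*

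**What the plan says.** Protocol 4.1.5 has two rules for an event whose intensity varies. Within a day: "When changes in the intensity of an AE occur more frequently than once a day, the maximum intensity for the experience should be noted". When the category changes across days: "those changes should be recorded separately (with distinct onset dates". The second rule does not distinguish worsening from improvement.

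SAP 7.12.1 then uses onset dates and counts. One listed output is "Overall incidence and the number of AEs, SAEs, TEAEs leading to withdrawal". On treatment periods it says: "A TEAE will be assigned to the treatment received immediately before onset". It adds a visit-based rule under which an onset from Visit 11 onwards belongs to T2. Its only rule on a change of severity across periods concerns an increase, which goes to the treatment received just before the increase. For repeated reports of one term it says: "If a subject reports AEs more than once within a SOC/PT, the AE with the worst-case severity will be used", and it confines this to the severity summaries.

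Protocol 4.2.1 treats a condition already present before the treatment period as an AE only if it then gets worse.

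Protocol 3.3.3 uses the word occurrence for AESIs at two levels. One occurrence "precludes the subject from receiving a repeat injection". Across the study, "Three occurrences of the AESI of the same type across the study will trigger stopping of all further dosing", pending a safety review.

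**The concern.** The recording rule creates several dated entries for one clinical event, and neither document says how they are rejoined before counting. The SAP's rules work on exactly the things the splitting multiplies: entries and onset dates. Two outputs are exposed.

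- The number of AEs would depend on how often an event changed grade as well as on how many events occurred.
- An event that began after the first injection and improves after the second would leave a lower-grade entry with a T2 onset date. Recovery from a T1 event would then be reported as a new event after the repeat injection.

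The safety of single and repeat dosing is a secondary objective (SAP 3.2), and SAP 7.3 shows AEs by treatment. With about a dozen subjects in T2, a few misplaced entries would be visible in that comparison.

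**Working it through.** The documents give no figure on this point, so there is none to reproduce. The check traces the stated rules.

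**Inputs.** Recording rule: Protocol 4.1.5. Counting and period rules: SAP 7.12.1. Worsening-only principle: Protocol 4.2.1. Subjects with both injections: 12 (SAP 5).

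**Step 1: records per event.** With k day-to-day changes of intensity category, records = 1 + k.

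| Course of one event | Changes k | Records |
|---|---|---|
| constant grade | 0 | 1 |
| mild, moderate | 1 | 2 |
| moderate, mild | 1 | 2 |
| mild, moderate, mild | 2 | 3 |
| severe, moderate, mild | 2 | 3 |
| mild, moderate, severe, moderate, mild | 4 | 5 |

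**Step 2: what the splitting changes within one period.** Subject incidence stays at 1 in every row. The severity summaries keep one worst-case record per subject and term, so they do not change either. The number of AEs has no such rule and takes the value in the last column.

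**Step 3: an event that crosses periods.** Take an event that is mild and then moderate in T1, is still present at the second injection, and eases to mild afterwards. It has three records, the last with an onset after the second injection.

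- That record meets the SAP's first TEAE criterion, which needs only an onset on or after the index injection.
- Both onset-based assignment rules place it in T2.
- The increase rule does not apply.
- Worst-case selection does not remove it if it is the subject's only T2 record for that term.

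The result is 3 AEs in the count, 1 subject in T1 incidence, 1 in T2 incidence and 1 overall, from one event.

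The two assignment rules also disagree in one window. Visit 11 is the T2 baseline and the injection is at Visit 12. Easing dated from Visit 11 until the injection is T2 by the visit rule, but T1 by the preceding-treatment rule.

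**Step 4: size.** One such subject, with no other T2 event of that term, moves T2 incidence by 1/12 = 8.3 percentage points, assuming about 12 subjects in the T2 column.

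**Step 5: Protocol 4.2.1 against the SAP.** The preceding sentence in 4.2.1 speaks of the time before the first dose, which suggests that the worsening-only sentence concerns entry to T1. On that reading it does not govern T1 versus T2. Read for each treatment period, it excludes the easing record that the SAP's onset rules admit. Neither reading settles the case.

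**The case against.** The strongest reply has three parts.

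1. Protocol 4.1.5 asks for changes to be recorded separately; it does not call each change a separate AE. The eCRF and the separate data management plan (Protocol 5.1) are not available to this review and may link the entries. This stands as a caution: absence of a link field cannot be inferred. However, the SAP's rules as written refer to onset dates and to no link.
2. The worst-case rule in SAP 7.12.1 removes most of the effect. It does so for the severity summaries, and subject incidence within a period was never affected. It does not reach the number of AEs or an entry placed in a different period.
3. An explicit rule for increases only, a second TEAE criterion that requires worsening, and Protocol 4.2.1 together imply that a decrease should stay in its original period. That is probably the intention. It is still an inference, and the stated onset rules give the other answer when followed literally.

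A reader might go further in two ways that the documents do not support.

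- **That one fluctuating AESI could by itself trigger the study-wide pause in dosing.** Three records reach the number three only if an occurrence means an intensity record. Protocol 3.3.3 counts occurrences of the AESI and never mentions eCRF records; separate events is the natural reading. Protocol 4.2.2 and 4.2.3 send AESIs through SAE reporting, where later information is handled as follow-up. An AESI in T1 also cannot carry into T2, because it bars that subject from the repeat injection.
- **That every T1 event easing in T2 becomes a spurious T2 event.** This requires the onset rules to be applied mechanically, against the text that points the other way.

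**Conclusion.** The point holds as an interaction of stated rules. Followed literally, Protocol 4.1.5 and SAP 7.12.1 count one fluctuating event as 1 + k AEs, and they can place an easing T1 event in T2.

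The effect is limited to the number of AEs and to the T1/T2 split of events that persist to Visit 11 or later and then ease. The second effect is about 8 points of T2 incidence per affected subject, assuming about 12 subjects in T2 and no other T2 event of that term in that subject. It needs an event still present when the second injection falls due, 4 to 8 weeks after the first; the documents give no basis for estimating how many there would be. The pharmacodynamic analyses are untouched.

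For the AESI rule, only a clarification is warranted: the unit of an occurrence is not defined.

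**What to change.** In SAP 7.12.1:

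- Link the intensity records of one event, by an eCRF identifier or a derivation.
- Count each linked episode once, at its maximum severity, in the number of AEs. This matches what Protocol 4.1.5 already does for changes within a day.
- State that a record showing a decrease keeps the episode's original onset date and period, and that only an increase is reassigned, as the SAP already says.
- Reconcile this wording with Protocol 4.2.1, and make the Visit 11 rule agree with the preceding-treatment rule.

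As a separate clarification, the sponsor should state in Protocol 3.3.3 the unit of an AESI occurrence, consistently with the recording rule in 4.1.5. The threshold is for the sponsor and is not questioned here.

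The cost is one link field or derivation step and a few sentences. The individual intensity records can stay in the listings, so no information is lost.

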4.2 Reporting Procedures and Requirements

4.2.1 Adverse Events

AEs occurring after the subject signs the ICF until the 30 days after the last study visit will be recorded. Any AEs occurring before the start of treatment (ie, before the first dose of the IP) will be recorded in the medical history. Also, the sign, symptom, or disease present before starting the treatment period are only considered AEs if they worsen after starting the treatment period.

If the investigator detects an AE in a study subject within 30 days after the last scheduled follow-up visit and considers the event possibly related or related to prior study treatment, the investigator should report it to the sponsor [REDACTED]

The investigator should report all AEs on the AE page(s) of the eCRF and source documents (if the eCRF is unavailable for direct data entry [DDE]), regardless of seriousness, severity, and causality. Whenever possible, an AE will be reported using a diagnostic term, (eg, “common cold” or “upper respiratory infection” rather than “runny nose, cough, mild fever”) and should be described with the attributes described in [Section 4.1.5](#).

4.2.2 Adverse Events of Special Interest

If any of the following AEs occur at a time after the procedure that are attributable (ie, possibly related or related) to IP should be reported in the eCRF and Medical Monitor is to be contacted immediately and the reporting procedures for SAEs is to be followed ([Section 4.2.3](#)):

- [REDACTED]
- [REDACTED]
- [REDACTED]

4.2.3 Serious Adverse Events

Each AE will be assessed to determine whether it meets seriousness criteria ([Section 4.1.2](#)). If the AE is considered serious, the investigator should report this event to [REDACTED] as outlined below and also to the Institutional Review Board (IRB) according to its standard operating procedures.

The investigator should report all SAEs to [REDACTED] on the eCRF within 24 hours of the Investigator, designee or site staff’s knowledge of the event regardless of relationship to study drug.

If the site experiences a temporary disruption of the eCRF system, a back-up paper SAE Report Form will be available for site staff to complete.

- Site staff will complete the paper SAE report form and email it within 24 hours to the following address: [REDACTED]
- Only in cases where the email system is unavailable, site staff will send the SAE by fax to: [REDACTED]

■ [REDACTED]

[REDACTED]

- [REDACTED]
- [REDACTED]
- [REDACTED]
- [REDACTED]

█ [REDACTED]

All recorded SAEs, regardless of relationship to study treatment, will be followed up until resolution, stabilization, or the subject is lost to follow-up and cannot be contacted. In circumstances where the Investigator is unable to contact the subject, the Investigator must provide a written statement to Semnur confirming that the subject is lost to follow-up. SAEs that are ongoing at EOS should be followed until resolved.

Additional follow-up information must be reported in the eCRF within 24 hours of awareness following Investigator (or site) awareness of the information. The Investigator should not delay reporting an SAE to obtain additional information. Additional information, when available, should be reported to [REDACTED] by the reporting procedures described above.

If the investigator detects an SAE in a study subject within 30 days after the last scheduled study visit, and considers the SAE related or possibly related to prior study treatment, the investigator should report it to sponsor [REDACTED]

The sponsor or its representative will be responsible for determining and in turn, reporting SAEs to regulatory authorities per the applicable regulatory requirements.

